- 4. **Bereavement.** Any bereavement within a household, independent of number of people left in the household within a specific period (lookback period to be determined). This variable will not apply to individuals living in care homes or at addresses where seven or more people are registered.
- 5. **Change: Multiple moves in last 12 months.** This is where a person changed address at least twice, as identified as having had three or more different pseudo-UPRNs, within 12 months.

For bereavement and recent change to living alone, before determining the lookback period we will first explore the time period that best characterises the patients that were enrolled in MDTs, ie affected treatment assignment. We will explore 3 and 12 months' lookback. Based on baseline characteristics, we will also determine whether to look at dementia or frailty for other household members.

We will start by examining whether there are differences in the social context variables at baseline between the original intervention and matched control patients, in each of the three studies individually. For those variables that look promising, we will quantify their effect on the outcomes for the original intervention and matched control groups, by including these social context variables in a subsequent outcome regression.

We may also explore five or fewer pre-specified two-way interaction effects, eg:

- recent bereavement with living alone
- mental ill health with bereavement
- mental ill health with recently living alone.

If these variables are shown to be important to adjust for we will include them in the entropy balancing and subsequent analyses, as appropriate.

We will also create a flag for whether the person died within 90 days of being enrolled in an MDT or being selected as a control, as a proxy for nearing their end of life. We will check for any imbalances between intervention and matched controls in this variable, which may suggest previously unobserved differences in disease severity or frailty that may confound emergency hospital admission rates. We will also check for any imbalances between intervention patients in the three studies, which would indicate heterogeneity.

We will create subgroups based on this EOL flag and check the balance between the intervention and matched control groups on patient characteristics.

Handling of differential information from risk scores

As previously noted, there were differences in what characteristics were matched on (eg risk scores in ECS and EPC studies but not in NEHF). It is likely that SMDs and other balance diagnostics across covariates will reveal imbalances between the studies upon stacking the sample; this is a particular issue because risk stratification used for determining treatment assignment in Fylde Coast (and therefore included in matching and regression there) was not used in NEHF.

ECS and EPC used the CPM,¹⁵ which derives risk scores from inpatient, outpatient, A&E, and GP data sources to inform eligibility and selection of patients to receive MDT services in the Fylde Coast.¹⁴ In NEHF, the intention was to similarly deploy the Johns Hopkins Adjusted Clinical Groupings (ACG) system.^{70,71} The ACG does not directly map onto the CPM in any case; however, due to technical and information governance constraints, the ACG risk stratification tool was not deployed in NEHF for the ICT during our study follow-up period, except for a small minority of patients in one of the five localities.¹³ As it had not been generated for the vast majority of individuals and did not inform their enrolment or case management of the ICT intervention, it was not included in the NEHF analysis, either in matching or regression stages.

Because the CPM is not straightforward to generate, it is not feasible for the IAU to carry this out for the NEHF sub-sample in order to make it generalisable with the Fylde Coast MDTs. Although CPM relies on conventional logistic regression for statistical modelling, it maps onto a complex set of predictive covariates from over 1,000 diagnostic codes, not only across Hospital Episode Statistics but also from general practice Read codes, which are not routinely available to the IAU. Notably, CPM has not been funded for continued development within the NHS since 2011, which is likely to impair the predictive value of its algorithms given major health system changes that have changed patterns of hospitalisation in England over the past decade.

Therefore, we will instead generate comparative effect estimates from the ECS and EPC samples using the entropy balancing algorithm as described below, but remove the risk scores that were used for matching and regression in the original Fylde Coast evaluations. Alongside other procedures as described above to map all variables across the three data sets, this will allow for greater comparability and would in principle standardise the risks of omitted variable bias when estimating results across Fylde ECS, Fylde EPC and the NEHF ICT.

Furthermore, as the IAU has already included past hospital activity from inpatient, outpatient and A&E data sources across the evaluations of these MDTs, much of the information used in the CPM risk score is already captured in our analysis (ie risk score is largely collinear with other SUS covariates already included in our analysis). We believe that the statistical value of including the CPM risk scores in Fylde Coast was primarily from inclusion of GP-level data, for instance on newly diagnosed LTCs recorded in primary care that had not yet been included in hospital-level records. In validation work on the successor model for the CPM, Billings et al had found that inclusion of GP data improved the predictive accuracy (as measured by the c-statistic) by an incremental amount, from 75.2% to 78.0% across the English patient sample of 1.8 million patients from five primary care trusts.⁶⁸

As a check on the robustness of our proposed approach to dealing with risk scores, we will pursue one of the following two options:

- 1. **Repeat outcome modelling** within the Fylde MDT sample, using a newly generated counterfactual from entropy balancing that excludes risk scores.

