The overall outcomes underpinning this study relate to emergency hospital use, as this analysis aims to understand why patients enrolled in MDTs have in general higher emergency hospital use than their comparison groups. While these measures are not the only informative outcomes for assessing the value and impact of integrated care, national and local health and care commissioners in the UK set out to reduce unplanned hospital use by establishing these MDTs in the community, to complement and in some cases replace routine primary care. Measures of unplanned hospital use are conventionally used to summarise the health services impact of interventions, particularly in England.^{54,55} Using common outcome measures allows for more straightforward comparison between different studies.

The primary outcomes to be examined are:

- rate of A&E attendances
- rate of emergency (non-elective) hospital admissions
- average emergency admission associated length of stay (LoS)
- rate of chronic ambulatory care sensitive (chronic ACS) emergency admissions
- rate of urgent care sensitive (UCS, also known as acute ACS or AACS) emergency admissions.

We will also examine:

rate of deaths (independent of whether they occurred in and outside of hospital), as
a diagnostic check. We use mortality rate as a 'placebo test', 'falsification', or 'negative
control' for potential unobserved confounding, ie to check that the treatment and
counterfactual groups are similar at baseline, as mortality risk may be a proxy for severity
of disease. We typically do not expect relatively short exposures to MDTs to materially
impact life expectancy. Prior evidence about MDTs and mortality is weak; based on
previous programme theory and evaluation, it may be the case that improved quality of
care through MDTs can delay death. Given the safety profile of MDT health coaching and
interventions to coordinate communication and care referrals, we would not expect that
MDTs plausibly increase deaths.

Patient subgroups

These analyses will be carried out for the overall population of MDT-treated patients and the counterfactual, alongside up to seven subgroup analyses to assess patient-level heterogeneity. These subgroups are pre-specified below on the basis of past research on MDTs and English policies that have identified these groups as suitable for community case management.⁸

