It is possible to identify further patient subgroups, but we have prioritised a set of seven key contrasts. Interpretation becomes more problematic whenever more subgroups are specified, and our statistical procedures are at greater risk of finding spurious 'significant' differences in impact purely by random chance due to multiple testing across many hypotheses using the same data set. This risk of multiple testing will be addressed by Dunn-Sidak corrections to hypothesis tests (as a more precise alternative to Bonferroni adjustment). We will report both the Dunn-Sidak corrected and uncorrected p-values arising from hypotheses tests of outcome modelling across the pooled sample and the pre-specified subgroups.

All below analyses will be undertaken as stratified subgroups, but will only be reported where there is a minimum sample size across the three evaluations of 50 MDT-treated patients and 250 potential control individuals, ie where statistical estimates are expected to be stable and reliable.

We will construct the counterfactual for the MDT-treated patients in each subgroup separately (unless otherwise specified below) using entropy balancing or inverse probability of treatment weighting (IPTW), used as appropriate.

- 1. **By social context:** based on the exploratory analyses for incorporating address-level data, we will determine the most useful subgroup based on the social context variables identified (eg living alone).

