The IPAEOPGP is a risk prediction model of hospital admissions that builds on and improves on earlier models such as the PARR algorithm and identifies a number of comorbidities predictive of hospital admission.^{68,69} Selected variables from IPAEOPGP identifiable in inpatient hospital records and not captured in the Elixhauser list were included in the list of potential baseline variables.

After this **stacked** data set is generated across MDT-treated units and control units originally selected within each study by genetic matching, we will run standard quality checks for completeness and plausibility across the sample, in order to avoid the inclusion of erroneous data. In certain cases, we may address missing data by appropriate multiple imputation or complete case analysis.

We will **divide the data set into the pre-specified subgroups detailed above** and check the sample sizes. Where **the pre-specified subgroups are too small** (ie fewer than 50 intervention patients across the stacked data), no further analyses on that subgroup will be done. This is because small sample sizes will compromise our ability to generate reliable and stable estimates of the impact of MDTs and there will be lower power to detect effects.

If, however, the pre-specified subgroups are large enough (at least n=50 interventions, and at least n=250 potential controls in the donor pool for weighting), we will address the subgroup analysis through creating new counterfactuals for each subgroup by reweighting using entropy balancing methodology as detailed above.

Exploratory data analyses: improving on unobserved confounding by exploring social context factors and a proxy for end of life

By using pseudonymised address information for all individuals registered with a GP from the NHAIS data and linking this to SUS, we will investigate the relevance of a number of variables relating to social context, which may be be proxies for social isolation, instability or other factors that may affect an individual's risk of emergency hospital use and may be a referral criterion for MDTs.

We will identify and explore a number of indicators:

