As in the original studies, we will **estimate outcomes** based on four sets of covariates: all 'base' covariates (as described in Table 5); a smaller set of 'core' covariates that exclude historic hospital activity; covariates selected from data-driven lasso regression; and unadjusted or crude results. The lasso is a variation of ridge regression that applies a machine learning algorithm to principled variable selection – additional terms are penalised such that included variables achieve an optimal and replicable signal-to-noise ratio and improves upon the ad hoc nature of previously conventional procedures such as stepwise selection.²³ The final model will always be adjusted for covariate unless the algorithm entirely failed to converge due to sparse data. The most appropriate generalised linear model, selected from several pre-specified distributions, and covariate list will be chosen based on the Akaike Information Criterion²⁴ and other diagnostics, such as comparing observed vs predicted zeros (for count variables), and root mean squared errors (RMSE). Depending on the outcome being modelled, the likelihood distributions used are typically Poisson or inverse negative binomial (for count outcomes) – potentially with some corrections for zero-values inflation or over-dispersion – or logistic (for binary outcomes).

For the overall pooled data set, we will generate generic **forest plots** per conventional meta-analytic summaries that depict the weighted ATT estimates from across the three evaluations, and also compare the results from fixed-effect vs random-effect models (where the latter will be more valid if the study samples contribute 'true' heterogeneity). The results of

the model fitting may also be reported as tabular effect estimates and 95% confidence intervals. We will also calculate and report commonly accepted measures for study heterogeneity in the meta-analysis, namely the *H* and *I*² statistics⁷³ as well as τ^{274} . We will also report the difference in effect estimates by fixed and random effects for the MDT treatment.

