We will initially identify subgroup effects based on the statistical significance and absolute magnitude of their coefficients during outcome regression. Where these terms are significant, we may carry out further post hoc stratified analysis by repeating the weighting algorithm for MDT patients in this subgroup only, in order to generate conditional effect estimates that may be of particular interest to policymakers in planning future targeted MDT implementation. In other words, we may run the entropy balancing algorithm up to seven times to obtain an appropriate counterfactual for each of the patient subgroups of interest. Combined with the reweighting of the overall MDT pool and each of the MDTs, this implies up to 15 sets of entropy balancing and/or IPTW results.

However, we will drop subgroup analyses where there appears to be poor 'overlap' of key characteristics such as age or gender distribution between the MDT patients and the reweighted controls. This is because such exchangeability between intervention and counterfactual populations is a prerequisite for the validity of treatment effect estimates.^{62,72}

For example, it will not be valid or useful to compare hospital activity among a population of MDT patients with dementia who are primarily female and over 70 with a population of control patients who are primarily male and under 50. Where exchangeability is poor, entropy balancing typically fails to converge due to data sparsity. PS or IPTW may converge but results should be interpreted cautiously due to the risk of model misspecification and biased estimates. As poor overlap signals missing data observations that would otherwise have to be entirely extrapolated, no statistical method can address this flaw if it arises.

In the event of non-significant regression coefficients, small sample sizes, poor intervention-counterfactual overlap, or other issues we may uncover during the exploratory analyses that constrain statistical feasibility, we will only carry out and report a smaller set of regression-adjusted subgroup analyses – where we are confident the results are meaningful and reliable (ie overlap appears to be satisfied and statistical models including many covariates are successfully fitted). We anticipate that some of the subgroups will most likely fail one or more of these conditions.

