For all analyses and finalised list of subgroup analyses, we will apply conventional meta-analysis techniques based on assumed homogeneity of effects. We would then generate **estimated treatment effect estimates across all three MDTs**. The effect estimates from the three studies should be more numerically **precise** due to the larger sample size available from pooling, and based on the previous ATTs we can already anticipate that for the overall study pool these will show an approximately 30% to 40% increase in the primary study outcomes (A&E attendances and emergency admissions).

We will generate forest plots depicting the outcomes from the 'stacked' data set, and also compare the results from fixed-effect vs random-effect models (where the latter will be more valid if the study samples contribute 'true' heterogeneity) as described above, but anticipate that this crude estimate will be less precise than the reweighted estimates described above.

Relatively poor balance from SMD plots or other exploratory diagnostics may suggest that a conventional approach to pooled analysis using the original combined data set is biased or invalid, for one or many of the results sets. Even if SMD plots and other diagnostics do not suggest imbalance, homogeneity of effects is a quite strong causal assumption that has been critiqued elsewhere.⁷⁶The effect estimates from conventional meta-analysis across a small sample of n=3 studies would therefore be relatively weak evidence regardless of ultimate effect estimates, and suggest hypotheses for further validation.

For this reason, we strongly prefer effect estimates generated from entropy balancing and appropriate reconstruction of counterfactuals across the sample of interest, as they provide much stronger evidence for causal inference about the impact of MDTs.

Patient and Public Involvement and Engagement (PPIE)

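### The planned Dunn-Sidak correction is valid but almost the same as Bonferroni; the Holm-Sidak step-down form controls the same error rate and never rejects fewer hypotheses

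*SAP*

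**What the plan says.** The SAP, under Methods: Patient subgroups, warns that more subgroups mean more chance findings, says "we have prioritised a set of seven key contrasts", and continues: "This risk of multiple testing will be addressed by Dunn-Sidak corrections to hypothesis tests (as a more precise alternative to Bonferroni adjustment". It adds: "We will report both the Dunn-Sidak corrected and uncorrected p-values arising from hypotheses tests of outcome modelling across the pooled sample and the pre-specified subgroups". No step-down procedure is mentioned, no family size is given and no family-wise alpha is stated.

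Other parts of the SAP bear on the point:
- Study endpoints lists five outcomes under "The primary outcomes to be examined are".
- Pooled and subgroup analyses counts the weighted analyses: "this implies up to 15 sets of entropy balancing and/or IPTW results". It plans to report "tabular effect estimates and 95% confidence intervals", which are ordinary intervals and not simultaneous ones. It also places the main value of pooling in subgroups that were too small within the single evaluations.
- The section on exploratory analyses of the stacked data concedes that in small subgroups "there will be lower power to detect effects".
- The section on conventional pooled analyses of the stacked data expects, for the overall pool, that "these will show an approximately 30% to 40% increase in the primary study outcomes".

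**The concern.** The correction is offered as an improvement on Bonferroni, but at any plausible family size the two are almost indistinguishable. In single-step form, every test must clear the strictest threshold, however many of the other hypotheses have already been rejected. A step-down version of the same correction removes that restriction without giving up error control.

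What is at stake is power in the smaller subgroups. Three original studies all found higher emergency use, and the plan expects the pooled result to do the same. If effects are tested within each subgroup, the large subgroups are likely to be rejected early, and the small ones could then be judged at milder thresholds.

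**Working it through.** The plan gives no adjusted threshold, family size or power for this point, so there is no figure of its own to reproduce.

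**Inputs.** From the SAP: seven subgroups (eight tests with the overall sample), five primary outcomes, up to 15 result sets, 5,411 MDT patients, and the Table 4 intervals for A&E attendances. Assumed: family-wise alpha 0.05 two-sided, the single-step reading, and the effect and subgroup sizes stated below.

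**1. Sidak against Bonferroni.** The thresholds are 1 − 0.95^(1/m) and 0.05/m.

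| m | Sidak | Bonferroni |
|---|---|---|
| 7 | 0.00730 | 0.00714 |
| 8 | 0.00639 | 0.00625 |
| 35 (7 × 5) | 0.001464 | 0.001429 |
| 40 (8 × 5) | 0.001282 | 0.001250 |
| 75 (15 × 5) | 0.000684 | 0.000667 |

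The Sidak threshold is 2.2% to 2.6% larger in relative terms. Family-wise error under independence is 0.0500 against 0.0488 to 0.0489. For a test with an assumed 80% unadjusted power, corrected power is 54.7% against 54.4% at m=7, and 33.8% against 33.5% at m=40.

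**2. Why step-down cannot do worse.** Order the p-values from smallest to largest. Holm-Sidak compares the j-th with 1 − 0.95^(1/(m−j+1)) and stops at the first failure. For m=7 the thresholds are 0.0073, 0.0085, 0.0102, 0.0127, 0.0170, 0.0253 and 0.05. The first equals the single-step threshold and the rest are larger, so whatever single-step rejects, step-down rejects too. Both rest on the same condition: independence, or the Sidak inequality for two-sided normal statistics. Simulation (100,000 runs per scenario; m=7, 35 and 40; correlation 0 and 0.5) found no run that contradicted this. Holm-Sidak family-wise error was 0.026 to 0.051, at or below 0.05 within simulation error, and it equalled the single-step value when all nulls were true.

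**3. Average power per false null, with an assumed 80% unadjusted power and correlation 0.**

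| m | False nulls | Single-step | Holm-Sidak |
|---|---|---|---|
| 7 | 2 | 0.548 | 0.560 |
| 7 | 4 | 0.548 | 0.589 |
| 7 | 7 | 0.547 | 0.665 |
| 35 | 10 | 0.352 | 0.363 |
| 35 | 35 | 0.352 | 0.410 |
| 40 | 40 | 0.338 | 0.392 |

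With correlation 0.5 and all nulls false, Holm-Sidak reaches 0.654, 0.443 and 0.424 for m=7, 35 and 40.

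**4. Illustration by subgroup size, m=7.** The Table 4 A&E intervals give log-scale standard errors:
- ECS: ln(1.38/1.15)/3.92 = 0.0465
- EPC: ln(1.52/1.28)/3.92 = 0.0438
- ICT: ln(1.54/1.16)/3.92 = 0.0723

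The pooled SE is 1/√(Σ 1/SE²) = 0.0292. Assume overlapping subgroups of 4,000, 3,500, 1,800, 1,500, 800, 250 and 150 MDT patients and a rate ratio of 1.35.

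*(a) Testing whether the effect is zero in each subgroup, with every effect real.* The expected z is ln(1.35)/(0.0292 × √(5411/n)), which is about 3.96, 2.21 and 1.71 for the three smallest. Simulated with independent tests (200,000 runs), power rises from 90% to 95% (n=800), 32% to 52% (n=250) and 17% to 35% (n=150). If the four largest subgroups have no effect, the n=250 group goes only from 32% to 34%.

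*(b) Testing whether a subgroup differs from the remaining patients, with a true difference of ln(1.35).* The SE becomes 0.0292 × √5411 × √(1/n + 1/(5411 − n)).
- One real difference: 29.8% to 29.9% (n=250), or 15.9% to 16.0% (n=150).
- Both of these real: 30.0% to 30.4%, and 16.1% to 16.5%.
- Three real (n=1,500, 800 and 250): the n=250 group goes from 30% to 34%.

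**The case against.** The strongest reply is that nothing in the plan is wrong. Sidak is exact under independence and Bonferroni slightly conservative, so describing Sidak as the more precise of the two is literally true. The correction is standard, valid and fixed in advance. This stands. A reader might infer that the method is invalid or that its justification is false, and the SAP supports neither inference.

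The second reply concerns size. A reader might also infer that small subgroups stand to lose about 20 points of power. That figure needs a non-zero effect in every subgroup and tests of zero effect within each. The plan's warning about chance findings is worded in terms of differences in impact between groups, and Pooled and subgroup analyses first screens subgroups by their regression coefficients. If all subgroups share the same 35% increase, every null of no difference is true and there is no power to gain. The plan also speaks of tests in the pooled sample and the subgroups, so both readings remain open. The assumed sizes are not in the SAP. They sum to 12,000 against 5,411 patients, so the groups overlap, although the tests were simulated as independent. The SE comes from the original matched studies, whereas the plan reweights the full control pool. This objection stands against the headline gain but not against the ordering of the two methods.

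Third, a single-step adjusted p-value depends only on its own test and m, which is convenient when subgroups may be dropped. It also has simple matching simultaneous intervals. The convenience is real but modest, and the plan proposes no such intervals. Because uncorrected p-values are also reported, a reader could compute Holm-Sidak if all of them appear.

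**Conclusion.** The point holds as a cheap improvement. The single-step correction is valid, practically the same as Bonferroni, and dominated by its step-down form. That ordering does not depend on the family size, the subgroup sizes or how many effects are real.

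The size of the gain does depend on them. For m=7 and the assumed sizes, it is up to about 20 points for small subgroups if all effects are non-zero, and about 0 to 4 points if the tests concern differences and few are real. At m=35 or 40, the average gain per false null is about 1 to 9 points under the 80% power assumption. All of this assumes a family-wise alpha of 0.05 and the single-step reading, which the SAP does not spell out.

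The choice of family moves the threshold far more than Sidak against Bonferroni does: 0.0073 at m=7 against 0.0013 at m=40. That is a separate gap, and it affects either procedure.

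**What to change.** In Methods: Patient subgroups, replace the Dunn-Sidak corrections with Holm-Sidak step-down adjusted p-values within the family of tests, reported beside the uncorrected p-values as already planned. The remark comparing the method with Bonferroni may stay.

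The cost is one sentence and one software option, and the SAP already provides for addenda. There are two downsides. Holm-Sidak has no simple matching simultaneous confidence intervals, and each adjusted p-value depends on the other tests in the family, so that family has to be settled before the adjustment is applied.

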- 2. By end-of-life status: contrasting the effect of MDTs between those individuals who died within 90 days of enrolment compared to those who did not.⁵⁶ This will explore whether the effect of MDTs on emergency hospital use differs between patients nearing the end of life and those that are not, as well as removing a potential source of unobserved confounding. Controls have previously been matched to these individuals in each of the three studies without accounting for information on death outcomes. Using contrasts from these pre-selected matched control groups within each study thus avoids endogeneity in sensitivity analysis for the possibility that death occurring within the 3 months after MDT enrolment (ie 'end-of-life' status) confounds MDT effects because it is a proxy for other unobserved medical or social risks among intervention users that were not present among matched controls. For a pooled sample, a similar procedure will be applied in which re-estimation of treatment effects will separately be conducted for the intervention patients who were at end of life and a reweighted counterfactual among the control pool. In other words, we construct the counterfactual for MDT-treated patients by weighting and matching only on pre-intervention characteristics, but we will compare the observed ATT to what is observed when splitting the treatment group into end-of-life and non-end-of-life populations.
- 3. By multimorbidity (LTCs):
 - 2+ comorbidities, as defined by Elixhauser records flags in hospital^{57,58} in the 3 years prior to study enrolment

4. By frailty:

• 1+ marker of frailty, as defined by the frailty index flags⁵⁹ from the same data

By specific comorbidity groups aligned with target groups identified as priority patients for integrated care and primary care quality improvement in the NHS Long Term Plan:⁸

- 5. **Dementia** as determined by the Charlson index⁶⁰
- 6. **Chronic pulmonary disease** as determined by the Elixhauser flag, as a proxy for 'respiratory diseases'⁵⁷
- Serious mental ill health, based on the definition used in the original NEHF evaluation^{*}, which was broadly based on the QualityWatch definition⁶¹

A subset of the mental ill health cohort who had at least one inpatient admission or outpatient appointment with a primary diagnosis of schizophrenia, bipolar disorder or psychosis (ICD-10 codes F20–29 and F30–31) (White et al, 2014) in a given year.

Exploratory analyses

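### The end-of-life estimate splits only the MDT patients by death within 90 days, so its end-of-life rate ratio is inflated even if MDTs have no effect

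*SAP*

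**What the plan says.** The estimation rule stands in one place, SAP, Methods: Patient subgroups, item 2 (By end-of-life status).

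- Within each study the comparators are the existing matched controls: "Controls have previously been matched to these individuals in each of the three studies without accounting for information on death outcomes".
- For the pooled sample, re-estimation "will separately be conducted for the intervention patients who were at end of life and a reweighted counterfactual among the control pool".
- In summary, "we construct the counterfactual for MDT-treated patients by weighting and matching only on pre-intervention characteristics", and then "we will compare the observed ATT to what is observed when splitting the treatment group into end-of-life and non-end-of-life populations".
- The justification offered is: "Using contrasts from these pre-selected matched control groups within each study thus avoids endogeneity in sensitivity analysis".

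Nothing in item 2 restricts or splits the controls by their own death. The general subgroup rule just above it gives way where an item specifies something else.

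Two other places describe the flag for both groups. The exploratory section on social context and a proxy for end of life will "create a flag for whether the person died within 90 days of being enrolled in an MDT or being selected as a control", form subgroups from it and check imbalance and baseline balance. The discussion of H1 speaks of subsetting by death after enrolment or study entry. Neither gives an effect estimator.

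Objectives, question 1, plans to test whether the intervention effect differs between end-of-life patients and all others. The Main analysis section on unobserved confounding repeats the comparison for the pooled sample.

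**The concern.** Death within 90 days is known only after enrolment. Under item 2 it selects MDT patients but not their comparators. MDT decedents are compared with controls who resemble them at baseline but mostly go on to live. MDT survivors are compared with controls who still include those about to die. Baseline weighting cannot reproduce the selection, because death is only partly predictable from baseline. The design therefore creates the endogeneity that the text says it avoids.

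At stake is the reading of a pre-specified subgroup and sensitivity analysis. If people use hospital more in their last weeks, the analysis reports a large MDT harm at the end of life whether or not one exists. The test between the two halves would then tend to find a difference that supports H3 (limited scope to reduce use near the end of life).

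**Working it through.** **Mortality inputs.** The SAP states no expected result for this analysis, so the only figure to reproduce is the EPC death contrast. Under H1, EPC crude mortality is 10.6%, which is 3.6 points above controls, so controls have 7.0%. The crude odds ratio is (0.106/0.894)/(0.070/0.930) = 1.575, against 58% higher in Table 4. It reproduces, so 10.6% is the EPC-arm rate.

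**Share dying within 90 days.** Assume a constant hazard over the EPC mean follow-up of 220 days (Table 3):

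- MDT: 1 − 0.894^(90/220) = 4.5%.
- Controls: 1 − 0.930^(90/220) = 2.9%.
- Table 3 includes only MDT patients enrolled for at least 28 days. If only 62 of the 90 days count, the shares are 3.1% and 2.0%.

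Across 2% to 4.5%, 5,411 MDT patients would include about 108 to 243 decedents. That exceeds the reporting minimum of 50, so the number of treated patients would not stop the result being reported.

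**Null ratio, closed form.** Let p be the share of controls dying within 90 days and k the decedents' emergency-use rate relative to survivors (an assumption; the SAP gives none). Assume mean follow-up of 59 days for decedents (midpoint of 28 and 90) and 225 for others; at p = 0.03 these average 0.03×59 + 0.97×225 = 220 days. Relative to survivors, the rate in unsplit controls is

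Rc = (p·k·59 + (1−p)·225) / (p·59 + (1−p)·225).

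With no MDT effect, the end-of-life ratio is k/Rc and the other half is 1/Rc. For p = 0.03 and k = 5: Rc = (8.85 + 218.25)/220.02 = 1.032, giving 5/1.032 = 4.84 and 1/1.032 = 0.97.

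**Simulation under no effect.** 5,411 treated, 130,000 controls, entropy balancing on two baseline covariates of which one partly predicts death, and no MDT effect on use or death. About 3.2% to 3.4% of the treated die within 90 days. The overall rate ratio stays at 0.99 to 1.00.

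| k | End of life, closed form (p = 2% to 4.5%) | Other half, closed form | End of life, simulated | Other half, simulated | End of life, both arms split, simulated |
|---|---|---|---|---|---|
| 1 | 1.00 | 1.00 | 0.98 | 1.00 | 0.98 |
| 1.5 | 1.49–1.50 | 0.99–1.00 | 1.49 | 0.99 | 0.99 |
| 2 | 1.98–1.99 | 0.99–1.00 | 1.96 | 0.99 | 0.97 |
| 3 | 2.93–2.97 | 0.98–0.99 | 2.86 | 0.98 | 0.98 |
| 5 | 4.77–4.90 | 0.95–0.98 | 4.79 | 0.96 | 1.00 |

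The spurious ratio tracks k and is absent only near k = 1. With both arms split by the same flag, the end-of-life ratio returns to 0.97–1.00 and the other half lies at 0.99–1.00.

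**Scale.** Table 4 gives rate ratios of 1.26 to 1.40 for A&E attendances and 1.27 to 1.43 for emergency admissions. An artefact at k = 1.5 already exceeds them.

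**The case against.** **The flag exists for controls.** The exploratory section and the H1 discussion define it in both groups, and the Pooled and subgroup analyses section first looks for subgroup effects in regression coefficients, which suggests a two-arm flag. This shows that the SAP is inconsistent and that the repair is at hand. It does not remove the defect: the exploratory section uses the flag only for imbalance and balance checks, and no passage replaces item 2's estimator.

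**The plan is candid about limits.** The Main analysis section says the end-of-life analysis cannot settle unobserved confounding alone and that hospital use might lie between MDT use and death. That stands. A reader might infer that this is the plan's main check of H1, but reweighting on social context has that role.

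**The survivors' estimate.** A reader might infer that the effect in 90-day survivors also shrinks markedly, so that end of life seems to explain the whole increase. Weighting decedents by heads would give 1/(1 + 0.03×4) = 0.89 at k = 5, turning a true 1.40 into 1.25. The documents do not support that: four of the five primary outcomes are rates and records are censored at death, so decedents supply little control person-time. On person-time, 1.40 becomes 1.40 × 0.969 = 1.36.

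**Splitting controls also conditions on an outcome.** True, and it remains a limitation. But the one-arm split already does so, asymmetrically. Study endpoints does not expect short MDT exposure to affect life expectancy materially; on that premise the two-arm split is the coherent contrast.

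**Conclusion.** The point holds for the end-of-life half. As item 2 is written, the end-of-life rate ratio is inflated by roughly k under no MDT effect: about 1.5, 2.0, 2.9 and 4.8 for assumed k of 1.5, 2, 3 and 5. The non-end-of-life half is only slightly biased downwards, 0.95 to 1.00 for k up to 5. The between-subgroup test would tend to report a false difference, bearing mainly on H3, and the statement about endogeneity is incorrect.

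The size rests on k, on constant-hazard mortality derived from EPC, and on the assumed 59 and 225 days of follow-up. The direction rests on analysis per unit time. If events were counted per person without person-time, the decedents' short follow-up would reverse the bias for smaller k (0.40 to 0.79 for k of 1.5 to 3). The estimate would be invalid either way.

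**What to change.** Reconcile item 2 with the exploratory section and the H1 discussion, before any effects are estimated:

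1. Apply the same 90-day death flag to both arms when effects are estimated, in the matched and the pooled data.
2. Compare MDT decedents with control decedents and MDT survivors with control survivors, each reweighted on baseline covariates.
3. Label the end-of-life contrast descriptive, because it conditions on death after enrolment.
4. Delete the sentence claiming that the procedure avoids endogeneity.

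The cost is SAP wording and one or two weighting runs. Control decedents will be few in the matched data: at an assumed 2% to 3%, the 774 NEHF control records would hold about 15 to 23, so single-study end-of-life contrasts will be imprecise.

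A day-90 landmark for survivors may be added as an optional sensitivity analysis, but the repair does not need it. It changes the estimand and loses events in the first 90 days and records with under 90 days of follow-up. That matters with mean follow-up of 202 days in the ICT study and 220 in EPC.
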